7.1.3. Relationship of Adverse Events to Study Drug

Related AEs are those for which the investigator selected "Related" on the AE eCRF to the question of "Related to Study Treatment." Relatedness will always default to the investigator's choice, not that of the medical monitor. Events for which the investigator did not record relationship to study drug will be considered related to study drug for summary purposes. However, by-participant data listings will show the relationship as missing.

7.1.4. Serious Adverse Events

Serious AEs (SAEs) will be identified and captured as SAEs if the AEs met the definitions of SAEs that were specified in the study protocol. SAEs captured and stored in the clinical database will be reconciled with the SAE database from the Gilead Patient Safety (PS) Department before data finalization.

7.1.5. Treatment-Emergent Adverse Events

7.1.5.1. Definition of Treatment-Emergent Adverse Events

Treatment-emergent AEs (TEAEs) are defined as 1 or both of the following:

• Any AEs leading to premature discontinuation of study drug.

7.1.5.2. Incomplete Dates

If the onset date of the AE is incomplete and the AE stop date is not prior to the first dosing date of study drug, then the month and year (or year alone if month is not recorded) of onset determine whether an AE is treatment emergent. The event is considered treatment emergent if both of the following 2 criteria are met:

- The AE onset is the same as or after the month and year (or year) of the first dosing date of study drug, and
- The AE onset date is the same as or before the month and year (or year) of the date corresponding to 30 days after the date of the last dose of study drug

An AE with completely missing onset and stop dates, or with the onset date missing and a stop date later than the first dosing date of study drug, will be considered to be treatment emergent. In addition, an AE with the onset date missing and incomplete stop date with the same or later month and year (or year alone if month is not recorded) as the first dosing date of study drug will be considered treatment emergent.

7.1.6. Summaries of Adverse Events and Deaths

Treatment-emergent AEs will be summarized based on the Safety Analysis Set.

7.1.6.1. Summaries of AE incidence in Combined Severity Grade Subsets

A brief, high-level summary of the number and percentage of participants who experienced at least 1 treatment-emergent AE (TEAE) in the categories described below will be provided by treatment group. All deaths observed in the study will also be included in this summary.

One of the primary endpoints of the study is the proportion of participants with TEAEs. Therefore, the number and percentage of participants who experienced at least 1 TEAE will be provided and summarized by SOC, HLT (if applicable), PT, and cohort:

• TEAEs

For the AE categories described below, summaries will be provided by SOC, PT, and cohort:

- TEAEs with Grade 3 or higher
- TE treatment-related AEs
- TE treatment-related AEs with Grade 3 or higher

CONFIDENTIAL

- TE SAEs
- TE treatment-related SAEs
- TEAEs leading to premature discontinuation of study drug
- TE AEs leading to death (i.e., outcome of death)

Multiple events will be counted only once per participant in each summary. Adverse events will be summarized and listed first in alphabetical order of SOC (and HLT within each SOC if applicable), and then by PT in descending order of total frequency within each SOC. For summaries by severity grade, the most severe grade will be used for those AEs that occurred more than once in an individual participant during the study.

In addition to the above summary tables, all TEAEs, TE SAEs, TE treatment-related AEs, and TE treatment-related SAEs will be summarized by PT only, in descending order of total frequency.

In addition, data listings will be provided for the following:

- All AEs, indicating whether the event is treatment emergent
- All TE treatment-related AEs
- All AEs with severity of Grade 3 or higher
- All SAEs
- All TE treatment-related SAEs
- All Deaths
- All AEs leading to premature discontinuation of study drug
- 7.1.6.2. Summaries of AE Incidence by Severity

A brief, high-level summary of the number of percentage of participants who experienced at least 1 TEAE in the categories described below will be provided by treatment group. All deaths observed in the study will also be included in this summary.

The number and percentage of participants who experienced at least 1 TEAE will be provided and summarized by SOC, HLT (if applicable), PT, and treatment group.

For the AE categories described below, summaries will be provided by SOC, PT, and treatment group:

• TEAEs by maximum severity

• TE treatment-related AEs by maximum severity

Multiple events will be counted only once per participant in each summary. Adverse events will be summarized and listed first in alphabetic order of SOC (and HLT within each SOC if applicable) and then by PT in descending order of total frequency within each SOC. For summaries by severity, the most severe severity will be used for those AEs that occurred more than once in a given participant during the study.

7.2. Laboratory Evaluations

Laboratory data collected during the study will be analyzed and summarized using both quantitative and qualitative methods. Summaries of laboratory data will be provided for the Safety Analysis Set and will include data collected up to the last dose of study drug plus 30 days for participants who have permanently discontinued study drug. The analysis will be based on values reported in conventional units. When values are below the LOQ, they will be listed as such, and the closest imputed value will be used for the purpose of calculating summary statistics as specified in Section 3.7.

A by-participant listing for laboratory test results will be provided by subject ID number and visit in chronological order for hematology, coagulation, inflammatory markers, serum chemistry, and urinalysis separately. It should be noted that the routine coagulation test will only be done for cohorts 5-7 at Screening and Day 10 or Discharge). Values falling outside of the relevant reference range and/or having a severity grade of 1 or higher on the DAIDS grading scale will be flagged in the data listings, as appropriate.

No formal statistical testing is planned.

7.2.1. Summaries of Numeric Laboratory Results

Descriptive statistics will be provided by cohort for each of the following laboratory categories and tests

- Hematology (Hemoglobin [g/dL]; Hematocrit [%]; Platelet Count [x10^9/L]; WBC [x10^9/L])
- Chemistry (ALT [U/L]; AST [U/L]; Glucose [mg/dL]; Serum Creatinine [mg/dL]; eGFR, Bedside Schwartz [mL/min/1.73m²])
- Coagulation (Prothrombin Time [PT] [sec]; Activated Partial Thromboplastin Time [aPTT] [sec]; Prothrombin International Normalized Ratio [INR])

as follows:

- Baseline values
- Values at each postbaseline time point

• Change from baseline at each postbaseline time point

A baseline laboratory value will be defined as the last measurement obtained on or prior to the date/time of first dose of study drug. Change from baseline to a postbaseline visit will be defined as the visit value minus the baseline value. The mean, median, Q1, Q3, minimum, and maximum values will be displayed to the reported number of digits; SD values will be displayed to the reported number of digits plus 1.

In the case of multiple values in an analysis window, data will be selected for analysis as described in Section 3.8.2.

One of the secondary endpoints is descriptive statistics of bilirubin concentrations in < 14 days old participants. If there are sufficient participants who are < 14 days old in the Safety Analysis Set then descriptive statistics for bilirubin will be repeated for the subset of participants who are < 14 days old when enrolled into their respective cohorts. In addition descriptive statistics for bilirubin will also be provided for the subset of participants who are \geq 14 days old when enrolled into their respective cohorts. A by-participant listing of bilirubin concentrations will be provided by subject ID number and visit in chronological order for the subset of participants who are < 14 days old as well the subset of participants who are \geq 14 days old when enrolled into their respective cohorts.

In addition, line plots showing the median (Q1, Q3) change from baseline at each postbaseline time point will also be provided for the following laboratory parameters:

- ALT (U/L)
- AST (U/L)
- Serum creatinine (mg/dL)
- eGFR, using the Bedside IDMS-traceable Schwartz formula (mL/min/1.73 m²)
- Total bilirubin (mg/dL)

Note: This will be produced only for participants who are ≥ 14 days old.

7.2.2. Graded Laboratory Values

The DAIDS Table for Grading the Severity of Adult and Pediatric Adverse Event, Version 2.1 (July 2017) will be used to assign toxicity grades (0 to 4) to laboratory results for analysis. Grade 0 includes all values that do not meet the criteria for an abnormality of at least Grade 1. For laboratory tests with criteria for both increased and decreased levels, analyses for each direction (ie, increased, decreased) will be presented separately. The DAIDS scale is available at the following location:

https://rsc.niaid.nih.gov/sites/default/files/daidsgradingcorrectedv21.pdf

7.2.2.1. Treatment-Emergent Laboratory Abnormalities

Treatment-emergent laboratory abnormalities are defined as values that increase at least 1 toxicity grade from baseline at any postbaseline time point, up to and including the date of last dose of study drug plus 30 days for participants who permanently discontinued study drug, or the last available date in the database snapshot for participants who were still on treatment at the time of an interim analysis. If the relevant baseline laboratory value is missing, any abnormality of at least Grade 1 observed within the time frame specified above will be considered treatment emergent.

7.2.2.2. Summaries of Laboratory Abnormalities

Laboratory data that are categorical will be summarized using the number and percentage of participants in the study with the given response at baseline and each scheduled postbaseline time point.

The following summaries (number and percentage of participants) for treatment-emergent laboratory abnormalities will be provided by lab test and treatment group; participants will be categorized according to the most severe postbaseline abnormality grade for a given lab test:

- laboratory abnormalities
- Grade 3 or 4 laboratory abnormalities

For all summaries of laboratory abnormalities, the denominator is the number of participants with nonmissing postbaseline values up to 30 days after last dosing date.

A by-participant listing of laboratory abnormalities will be provided by subject ID number and visit in chronological order. This listing will include all test results that were collected throughout the study for the lab test of interest, with all applicable severity grades displayed.

Abnormalities in coagulation parameters will be graded for INR, PT, and aPTT.

For the INR of prothrombin time and aPTT, protocol specified toxicity grading scale depends on the upper limit of normal range (ULN). While the ULN of INR and aPTT depends on whether the participant is taking anticoagulant medication or not (ie, Not taking oral anticoagulant: 0.8 - 1.2; Taking oral anticoagulant: 2.0 - 3.0), this information is not collected by the reference laboratory. As a result, INR and aPTT will be graded by assuming participant is not taking an oral anticoagulant, which is a conservative approach that may lead to over-reporting of abnormalities for INR and aPTT.

7.2.3. Liver-related Laboratory Evaluations

Liver-related abnormalities after initial study drug dosing will be examined and summarized using the number and percentage of participants who were reported to have the following laboratory test values for postbaseline measurements:

- AST > 3 x upper limit of reference range (ULN)
- ALT > $3 \times ULN$
- AST or $ALT > 3 \times ULN$
- Total bilirubin $> 2 \times ULN$
- Alkaline phosphatase (ALP) > 1.5 x ULN
- AST or ALT > 3 x ULN and total bilirubin > 2 x ULN

The summary will include data from all postbaseline visits up to 30 days after the last dose of study drug. For individual laboratory tests, participants will be counted once based on the most severe postbaseline values. For both the composite endpoint of AST or ALT and total bilirubin, participants will be counted once when the criteria are met at the same postbaseline visit date. The denominator is the number of participants in the Safety Analysis Set who have nonmissing postbaseline values of all relevant tests at the same postbaseline visit date. A listing of participants who met at least 1 of the above criteria will be provided.

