12. APPENDICES

Appendix 1.Study Procedures Table

					Adı	ninistratio	n Period ^ь					Follow-up Period
	Screening	Baseline/ Day 1ª	Day 2	Day 3	Day 4	Day 5	Day 6	Day 7	Day 8	Day 9	Day 10	Day 30 (± 5 days)
Assent/Parent or Legal Guardian consent	Х											
Inclusion/Exclusion criteria	Х											
Focused medical history	Х											
Documentation of SARS-CoV-2 confirmation by PCR	Х											
ECG	Х											
Complete or symptom-directed physical examination	Х	X	X	X	X	Х	Х	X	Х	Х	Х	X
Body weight ^c	Х	Х	X	Х	X	Х	Х	X	Х	Х	Х	X
Height/Length	Х											Xd
Head circumference and last recorded Apgar score if < 24 hours of age	Х											X ^d
Birth weight and gestational age if < 56 days	х											
Vital signs (heart rate, temperature, blood pressure [MAP if available, systolic and diastolic], respiratory rate, oxygen saturation)	Х	Х	x	X	х	Х	X	x	Х	Х	х	X
Documented respiratory status	Х	X	X	X	X	Х	Х	X	Х	Х	Х	X

			Administration Period ^b							Follow-up Period		
	Screening	Baseline/ Day 1ª	Day 2	Day 3	Day 4	Day 5	Day 6	Day 7	Day 8	Day 9	Day 10	Day 30 (± 5 days)
If available, record chest radiographic impression (or other imaging) but not mandatory to perform otherwise	Х	Х	х	Х	Х	Х	Х	x	Х	х	х	
Tanner Stage assessment if ≥ 6 years of age		Х										
Hematology, chemistry, urinalysis	Х		X			Х			Х		Х	Xe
Routine coagulation test (Days 5 and 10 only for Cohorts 5-6 and Day 10 only for Cohort 7)	Х		X			Х			Х		Х	
Inflammatory Markers (D-dimer, Ferritin, qCRP, Procalcitonin, and IL-6)	Х		X			Х			Х		Х	
ESR If ≥4 kg (Cohorts 1-4 only)	Х		X			Х			Х		Х	
Neonatal bilirubin panel for all neonates < 14 days, and any neonate presenting with jaundice	Х										Х	
Serology for SARS-CoV-2 if $\geq 12 \text{ kg} (\text{IgG, IgM, and IgA})^{f}$	X					Х					X	X
Pregnancy test (urine/blood)	Х											

			Administration Period ^b							Follow-up Period		
	Screening	Baseline/ Day 1ª	Day 2	Day 3	Day 4	Day 5	Day 6	Day 7	Day 8	Day 9	Day 10	Day 30 (± 5 days)
Nasopharyngeal and oropharyngeal samples (combined), rectal or fecal swab, and ET aspirates (if intubated) for SARS-CoV-2 PCR testing and possible viral sequencing ^f		Х		X		Х		X			Х	
Pediatric Early Warning Score Improvement Scale ^g	Х	Х	X	X	Х	Х	Х	X	Х	Х	Х	
Ordinal Scale	Х	X	X	X	X	Х	X	X	Х	X	X	
Plasma PK assessmentsh			X	X		X						
IV RDV administration		Xi	Xj	Xj	Xj	Xj	Xj	Xj	Xj	Xj	Xj	
Concomitant medications	Х	X	X	X	X	Х	X	X	Х	X	X	X
Adverse events ^k	Х	X	X	X	X	Х	X	X	Х	X	X	X

CCI

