Appendix 2. Pediatric Early Warning Score

Appendix 3. Programming Specifications

1) If the age from the Day 1 eCRF is not available, age will be calculated as follows:

Only year is provided for the date of birth (DOB). Use July 1 for the month and day.

- a) AGE (years) is calculated from the number of days between the DOB and Study Day 1,
- b) Use the SAS INTCK function to determine the number of "1st-of-month days" (eg, January 1st, February 1st, March 1st) between DOB and Day 1 (inclusive),
- c) Divide the result in (b) by 12, AGE = the integer of the result in (c), Age for laboratory test reference range will be based on the age at the sample collection date.
- 2) All screened participants refer to all participants who are screened (ie, with non-missing screening date) and have a screening number. For summaries the same participant is counted only once.
- 3) Screen failure participants are the participants who were screened and answered "No" for any inclusion criteria or "Yes" for any exclusion criteria regardless of which version of protocol the participant was consented to.
- 4) Participants in the All Enrolled Analysis Set are defined as participants enrolled into the study. IXRSRAND is the source to determine whether the participants is enrolled (ie, participant with non-missing ENRDTN in the IXRSRAND dataset), and confirmed by the eCRF ENROLL dataset (ie, ENROLLYN = "Yes" in ENROLL dataset).
- 5) Enrolled treatment (ie, TRT01P in ADSL) is derived from IXRSRAND, while actual treatment received (ie, TRT01A in ADSL) is assigned as the enrolled treatment if the participant took at least 1 dose of study drug and assigned as blank if the participant was never dosed.
- 6) In the disposition table, the reasons for premature discontinuation are displayed in the order as they appear on the eCRF.
- 7) Body mass index (BMI)

BMI will be calculated only at baseline as follows:

- BMI = (weight [kg]) / (height [meters]²)

Baseline height and weight will be used for this calculation if available.

8) Details of additional COVID-19 medications are provided in table below.

Drug name	ATC Code	WHODRUG Preferred Term
Chloroquine	P01BA	CHLOROQUINE
Hydroxychloroquine	P01BA	HYDROXYCHLOROQUINE
Lopinavir/ritonavir	J05AR	LOPINAVIR/RITONAVIR
Ribavirin	J05AP	RIBAVIRIN
Bamlanivimab/Etesevimab		BAMLANIVIMAB/ETESEVIMAB
Casirivimab/Imdevimab		CASIRIVIMAB/IMDEVIMAB
Molnupiravir		MOLNUPIRAVIR

Table 13-1.Additional COVID-19 Medications

ATC = anatomical therapeutic chemical

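### The under-14-day bilirubin summary, a secondary endpoint, depends on undefined sufficient numbers, and the liver table drops the 14-day split and ignores baseline

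*SAP*

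**What the plan says.** **Section 7.2.1 (numeric laboratory results).** The SAP states: "One of the secondary endpoints is descriptive statistics of bilirubin concentrations in < 14 days old participants". The next sentence attaches a condition: "If there are sufficient participants who are < 14 days old in the Safety Analysis Set then descriptive statistics for bilirubin will be repeated". No number defines sufficient. The companion summary for participants aged 14 days or more at enrolment carries no such condition. A by-participant listing covers both age groups and is also unconditional: "A by-participant listing of bilirubin concentrations will be provided by subject ID number and visit in chronological order". A note under total bilirubin limits the line plot to children of at least 14 days.

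**Section 7.2.3 (liver-related evaluations).** Six criteria are tabulated on postbaseline values up to 30 days after the last dose. They include total bilirubin above 2 x ULN on its own and the composite "AST or ALT > 3 x ULN and total bilirubin > 2 x ULN". For the composite, "participants will be counted once when the criteria are met at the same postbaseline visit date". The population is not restricted by age: "The denominator is the number of participants in the Safety Analysis Set who have nonmissing postbaseline values of all relevant tests". Baseline values play no part.

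**Related text.** Table 1-1 and Section 1.2 give Cohort 6 (0 to under 14 days, term) and Cohort 7 (0 to under 56 days, preterm) no minimum number. Appendix 3 says "Age for laboratory test reference range will be based on the age at the sample collection date". The procedures table in Appendix 1 has a "Neonatal bilirubin panel for all neonates < 14 days, and any neonate presenting with jaundice" at Screening and Day 10.

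**The concern.** There are two separate weaknesses.

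1. A named endpoint rests on a judgement made once the data are visible, in an open-label study and in cohorts that may be very small. If the condition is judged not to be met, no numeric under-14-day bilirubin summary remains. The word *repeated* does not help, because the chemistry tests listed for routine summary in Section 7.2.1 (ALT, AST, glucose, creatinine, eGFR) do not include bilirubin.

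2. Section 7.2.1 recognises that bilirubin in the first two weeks of life needs separate handling, and Section 7.2.3 does not carry this over. A table presented as showing liver abnormalities after initial dosing can therefore include a newborn whose bilirubin was already above the limit before dosing. At stake is the safety reading in the youngest participants, where each child carries a large share of the group.

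**Working it through.** The SAP states no figure for this point, so the check sets its sections side by side. The arithmetic is illustrative.

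**Step 1. Is the condition likely to bite?** Table 1-1 plans 4 x 12 + at least 4 = at least 52 participants in Cohorts 1 to 5. Cohorts 2 to 4 start at 28 days and Cohort 5 at 14 days. Among the cohorts whose ages are shown, children under 14 days can come only from Cohorts 6 and 7, planned as whatever is available. Zero, one or two such children is compatible with the plan.

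**Step 2. How is baseline treated across the laboratory tables?**

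| SAP section | Bilirubin rule | Baseline used? | 14-day split? |
|---|---|---|---|
| 7.2.1 | Numeric summary, listing, plot | Change from baseline | Yes, by age at enrolment (plot: 14 days or more only) |
| 7.2.2.1, 7.2.2.2 | Graded abnormality | Yes, rise of at least one grade | No |
| 7.2.3 | Above 2 x ULN | No | No |

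Take a newborn above 2 x ULN at Screening whose grade does not rise afterwards but who is still above 2 x ULN at Day 10. The child is absent from the treatment-emergent table and present in the Section 7.2.3 bilirubin-alone row.

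**Step 3. Does the age at which the ULN is taken matter?** Let B0 and U0 be bilirubin and ULN at baseline, and B1 and U1 the same at a later sample. A child not meeting the criterion at baseline (B0 <= 2 x U0) who meets it later (B1 > 2 x U1) must have B1/B0 > U1/U0. With falling bilirubin this can happen only if the ULN falls proportionally more than the bilirubin. As an assumed example, a ULN of 12 falling to 1.2 mg/dL and bilirubin falling from 8 to 4 mg/dL gives 8/12 = 0.67 x ULN, then 4/1.2 = 3.3 x ULN. With one ULN at both times, a fall cannot create a new case. The SAP gives no ULN and does not say whether the ranges have bands in days of life, so this step shows a possibility only.

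**Step 4. Which age should define the split?** Age at Day 10 is age at Day 1 plus 9 days. A child enrolled at 5 to 13 days is therefore at least 14 days old at the Day 10 sample. A split by age at sample would move that child to the older row and leave the case in Step 3 there. Age at enrolment, as in Section 7.2.1, keeps the child in one group.

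**Step 5. Bound on the overall row.** Let m be the number of participants under 14 days (assumed). Suppose all m meet the bilirubin-alone criterion, nobody else does, the rest number 52 and all have bilirubin values. The overall row then reads m/(52 + m):

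| m | Overall row | 95% upper limit for 0/m, 1 - 0.025^(1/m) |
|---|---|---|
| 1 | 1/53 = 1.9% | 97.5% |
| 2 | 2/54 = 3.7% | 84.2% |
| 3 | 3/55 = 5.5% | 70.8% |
| 5 | 5/57 = 8.8% | 52.2% |
| 10 | 10/62 = 16.1% | 30.8% |

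More participants outside this group would lower the middle column; missing bilirubin values among the others would raise it. The last column shows how little a percentage says at these sizes.

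**The case against.** The strongest defence is that the plan already contains most of the protection needed. The composite cannot be met by raised bilirubin alone. Reference ranges follow age at sampling, so the plan does not prescribe one fixed ULN. Results are shown by cohort (Section 3.2), and Cohort 6 is exactly the under-14-day term group. Total and direct bilirubin are both graded, with a rise from baseline required. Everyone meeting a liver criterion is listed, and the newborn bilirubin listing is unconditional. With one to three children, a median and range add little to that listing. The study is single-arm and descriptive, with no formal testing.

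Much of this stands, and it rules out stronger readings. A reader might infer that newborn jaundice will be reported as serious liver injury, or that real excess will be missed. Those are opposite outcomes under different ULNs, and the SAP gives no ULN, so neither is shown. A reader might also infer that the secondary endpoint is lost; the values will still be listed.

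What does not stand is that nothing needs changing. A listing is not the descriptive summary by which the SAP itself defines the endpoint. Cohort 7 mixes ages on both sides of 14 days, so cohort rows do not separate them. Listings allow case review but leave the tabulated percentages as they are. For INR and aPTT, Section 7.2.2.2 states its ULN assumption and warns of over-reporting; newborn bilirubin gets no such statement.

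**Conclusion.** The point holds in a limited form. The undefined condition on a named secondary endpoint is a plain defect of specification. The missing age split and baseline status in Section 7.2.3 mean that jaundice present before dosing can be counted in the bilirubin-alone row as an abnormality after dosing. The composite is much less exposed.

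No rate of miscounting can be given. It depends on how many children under 14 days are enrolled, on their baseline bilirubin and on the laboratory age bands, none of which the SAP supplies. Under the assumptions of Step 5, the effect on the overall row is at most 1.9% with one such child and 8.8% with five. It is larger within Cohorts 6 and 7 and absent from the rows of Cohorts 1 to 5. No formal conclusion of the trial turns on it. The case for change is that the remedy is cheap and bears on the safety reading in the youngest children.

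**What to change.** - **Section 7.2.1:** delete the condition about sufficient participants. Always give n, median and range of bilirubin by visit for participants under 14 days at enrolment, alongside the existing summary for those of 14 days or more.
- **Section 7.2.3:** report the total-bilirubin row and the composite row separately for participants under 14 days and 14 days or more at enrolment. This is the age rule of Section 7.2.1, and it also divides the mixed-age Cohort 7.
- **Section 7.2.3:** state beside each of these rows how many participants already met the criterion at baseline.
- **Section 7.2.3 listing:** flag participants whose reference range changed between the baseline sample and the qualifying sample.

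The cost is SAP wording and one split table, using data the plan already collects. If the SAP is already final, Section 1 provides for documenting the change in the CSR. The downside is very small numbers in the under-14-day rows, so counts should be read together with the listing. No clinical threshold is altered.
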